## II. *Benefits*

These studies are expected to add to the knowledge base on potential interventions for alcohol use. In addition, the mindfulness and tDCS application is expected to significantly decrease drinking for participants in the active condition and is also likely to reduce drinking in the mindfulness + sham condition. Given only a slight risk to participants and the greater possibility of long-term benefits to the knowledge base and to treatment interventions for AUD, the risks/benefits ratio seems reasonable. From a larger perspective, the findings of this investigation will increase the body of knowledge about the efficacy of a novel intervention for at-risk drinking and more broadly, will advance a biobehavioral conceptualization of treatment for AUD. The current research will address several gaps in the treatment literature with regard to the potential effects of mindfulness-based approaches for AUD. Although research has supported mindfulness-based relapse prevention (MBRP) as an effective intervention, our preliminary data suggests that its efficacy may be augmented by the addition of transcranial direct current stimulation to enhance engagement with treatment, increase rates of abstinence, and potentially further reduce heavy drinking. Further, the proposed study will assess behavioral mechanisms of change. Considering these clinically relevant and innovative study goals as well as the potential individual and societal benefits, the knowledge that may be gained in the current study will outweigh the risks for individual participants.

## III. *Privacy of Participants*

All consent procedures and experimental procedures will be conducted in offices maintained by the study investigators with appropriate privacy procedures (e.g. locked doors, opaque window coverings, and soundproof offices) in place. All PHI will be password protected and stored on a secure database accessible only by approved study personnel who are CITI certified in HIPAA confidentiality. While the nature of the research dictates that data cannot be collected anonymously, additional safeguards will be put in place to protect against breach of confidentiality. Each participant will be assigned a unique ID code at screening. All assessments for a given participant will be coded with his/her ID code. Questionnaire data will be collected using the Mind Research Network COINS system, hosted on a secure Mind Research Network server supporting 128-bit encryption and protected both physically (located in a locked room) as well as electronically using the most up-to-date security software available. Other data will be retained at the UNM Psychology Clinical Neuroscience Center (PCNC) in locked file cabinets and on password protected electronic files on computers with restricted access. A

single master list linking participant names and ID codes will be stored onsite in a separate locked file cabinet, and will only be available to research staff. Further, a Certificate of Confidentiality, which provides additional protection against obligatory release of confidential information, will be obtained from the Department of Health and Human Services prior to participant recruitment.

#### IV. *Unanticipated Problems/Adverse Events*

We would terminate the study if we found there were significant unanticipated adverse consequences for participation. For example, we would terminate the study if we found statistically significant preliminary results indicating that participants receiving the active tDCS were drinking at a higher rate than those in the sham condition. Analyses to compare sham versus active tDCS treatment efficacy will be conducted in February 2018, after a sufficient number of subjects have been treated, and at the time of submitting our annual progress report to NIH, which will occur in June 2018. We would also terminate the study if we became aware of any publications with such findings in other studies. Any unanticipated problems or adverse events will be reported to the IRB promptly and within 7 days of occurring.

### STUDY DATA

---

#### I. *Data Management Procedures and Confidentiality*

Online surveys and data collection forms have been used in our previous studies, and will be re-tested prior to utilization. Data are monitored on a daily basis during the baseline period to track response rates, evaluate success of the randomization procedure for producing equivalent groups, and assess data quality. Data are monitored on a weekly basis during each follow-up assessment period. Data cleaning is minimal because COINS has safeguards in place to minimize data entry errors. All data will be inspected continuously throughout the trial by a RA who is familiar with potential problems with data acquisition. All data will be double-checked by two independent persons. Scoring syntax that was developed for our prior studies will be used to produce summary variables, and standard procedures will be utilized for dealing with missing data.

We have taken a number of measures to ensure the confidentiality and integrity of the data and the safety of the participants. As described in the protections for human subjects sections above, all data from the proposed study will be identified by a numerical ID code only, which will be assigned during the phone screening. After phone screening, the phone screening form will be destroyed for those who are not eligible, although first and last names will be recoded to prevent re-screens and the demographic information and reasons for ineligibility for those who are ineligible will be recorded in a separate document without identifiers for reporting purposes. For eligible individuals the phone screening form will be de-identified and only linked to the participant with the participant ID code. The information linking the numerical participant ID code to identifying information will be maintained separately in a locked filing cabinet and kept separate and secure from the de-identified. All identifying information will be stored in a separate encrypted and password protected file and will not be linked with the screening or assessment data. At the conclusion of the study, the list linking the ID code to identifying information will be destroyed. Further, a Certificate of Confidentiality, which provides additional protection against obligatory release of confidential information, will be obtained from the Department of Health and Human Services.

## II. *Data Analysis/Statistical Considerations*

**Power analysis and sample size considerations.** We conducted power analyses using effect sizes from a pilot study ( $d=0.64$  and  $d=0.43$  on drinks per drinking day at post- and 2-month follow-up). With desired power  $>0.80$ , a two-tailed  $\alpha < 0.05$ , and three time-points, we will need 70 participants to detect a medium effect of active tDCS + MBRP vs. sham tDCS + MBRP on drinks per drinking day at follow-up. For mediation analyses we will need 74 participants to detect a medium effect. Attrition of 15% is anticipated based on our pilot tDCS study and thus we propose to recruit  $n=86$  participants to allow for some attrition. We anticipate screening up to 350 participants in order to recruit a sample of 86 participants.

**Data Analyses and Missing Data.** The primary study aim is to test the overall efficacy of the active tDCS + MBRP intervention compared to a sham tDCS + MBRP group. We will use maximum likelihood estimation for all analyses, which provides the variance-covariance matrix for all available data and is the preferred method for estimation when some data are missing. Variables associated with missing data and those used in randomization (gender, age, treatment history) will be covaried in all analyses.

**Aim #1: Efficacy Analyses.** All assessment data will be analyzed for outliers and missing cases to detect any bias that might result from differential attrition. The efficacy of active tDCS + MBRP versus sham tDCS + MBRP will be examined using a generalized linear mixed model with drinks per drinking day at the end of treatment and follow-up as the primary outcomes. We hypothesize active tDCS will be associated with significantly larger reductions in drinks per drinking day following treatment, as compared to sham tDCS. Interim analyses to compare sham versus active tDCS treatment efficacy will be conducted in February 2017, after a sufficient number of subjects have been treated, and at the time of submitting our annual progress report to NIH, which will occur in June 2017.

**Secondary Aim: Mediation Analyses.** Mediation models will be estimated for weekly and post-treatment assessments of mindfulness, inhibitory control, cue reactivity and craving, and negative affect using the product of coefficients method. We will look at self-report and behavioral assessments of each proposed mediator in separate analyses and we will also examine whether latent variables of each construct provide an adequate fit and can be used in the analyses. The mediated effect will be obtained by multiplying coefficients for the regression of the mediators (either separate measures or latent constructs) on treatment condition and for the regression of drinks per drinking day at the 2-month follow-up on the mediators. We will use bootstrapping to obtain 95% confidence intervals of the mediated effect. We hypothesize the effects of active tDCS on drinks per drinking day will be mediated by greater mindfulness, greater inhibitory control and reductions in cue reactivity, craving, and negative affect in the active tDCS group, as compared to sham tDCS.

**EEG Analysis.** EEG analyses will focus on the association between EEG biomarkers (e.g., resting state alpha, theta, beta, and gamma activity, P3 amplitude during tasks) and drinking outcomes, as well as changes in behavioral task performance. Data will be analyzed using MATLAB-based signal processing toolboxes (e.g., EEGLAB, ERPLAB, EEGIFT). We hypothesize significantly increased P3 amplitudes during cognitive inhibition and reduced P3 amplitude in response to alcohol cues in the active tDCS group at post-treatment, as compared to sham tDCS.

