## OBJECTIVES/AIMS

---

The goal of this study is to examine the efficacy of a MBRP and tDCS intervention in reducing drinking and impacting mechanisms of behavior change among individuals who are interested in reducing their alcohol drinking. The aims of the proposed research are:

**Primary Aim: To examine the efficacy of a mindfulness-based intervention, in combination with active tDCS (up to 2.0 milliamp (mA)) versus sham (0.0 mA) tDCS of the right inferior frontal gyrus (rIFG), in reducing drinks per drinking day.**

Individuals who are interested in reducing their drinking will be recruited from the community and clinician referrals. All participants will receive group MBRP for 8 sessions with each session lasting 2 hours, for up to 8 weeks, and will also be randomized to receive active up to 2.0 mA tDCS or sham 0.0 mA tDCS. Participants will complete weekly self-report measures during treatment and self-report, behavioral, and EEG assessments at baseline, end of treatment, and two months following treatment.

Hypothesis 1. Active tDCS, as compared to sham tDCS, will be associated with significant reductions in drinks per drinking day after treatment and 2 months following treatment.

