### *VIII. Participant Compensation*

We propose an incentive structure to maximize compliance that is consistent with other successful tDCS studies conducted by the investigative team. Participants will be paid up to \$20/hour for their participation during assessments: baseline (up to \$100), session questionnaires during 8-sessions of treatment (\$80), post-treatment (up to \$100), and 2-month post-treatment (up to \$40), plus an additional \$10 bonus for completing the post-treatment assessment, a \$20 bonus for completing the 2-month follow-up assessment, and a \$50 bonus for completing all assessment sessions, making the maximum compensation \$400. To increase retention, participants will be asked to provide addresses,

phone numbers, and email addresses, as well as the names and phone numbers for friends and family members who “*will always know where you are.*” We have used these methods in our prior studies and achieved 87.5% or greater follow-up rates.

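### Recruiting 86 leaves about 73 at 15% attrition, one short of the 74 stated for mediation, and the medium mediation effect behind 74 is never given a value

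*Combined protocol and SAP*

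**What the plan says.** The power paragraph in section II, Data Analysis/Statistical Considerations, gives 70 participants for the primary comparison on drinks per drinking day, at power above 0.80 and a two-tailed 5% level. It then gives the mediation requirement: "For mediation analyses we will need 74 participants to detect a medium effect". On losses it says: "Attrition of 15% is anticipated based on our pilot tDCS study". It proposes recruiting 86 on that basis and expects to screen up to 350 people "in order to recruit a sample of 86 participants".

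No path coefficient, d, correlation or f² accompanies the mediation figure, and no power or significance level is stated specifically for it. The only numerical effects in the paragraph are the pilot values d = 0.64 and d = 0.43, both for drinks per drinking day.

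The Mediation Analyses paragraph defines the mediated effect as a product of two coefficients: mediator on treatment condition, and 2-month drinking on mediator. The interval is a bootstrap 95% interval of unspecified type. The Participant Compensation section reports that the same retention methods "achieved 87.5% or greater follow-up rates" in earlier studies.

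**The concern.** Two separate things look wrong.

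First, the recruitment number does not deliver the stated requirement at the plan's own attrition rate. It looks as though 15% was added to 74, when 74 should have been divided by the 85% expected to remain.

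Second, the treatment is a two-arm factor, so the first mediation path is a difference between arms. The preceding sentence of the plan uses the same phrase, medium effect, for a comparison of the two arms, so many readers will take it as a d of about 0.5. On that reading 74 falls well short of 80% power.

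What is at stake is the interpretation of Hypothesis 2. The Background calls the study sufficiently powered. If true mediator effects are near d = 0.5, a mediated effect that is not statistically significant is about as likely as a significant one, and readers who trust the 74 could take it as evidence against the mechanism.

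**Working it through.** **Inputs from the plan.** 74 for mediation, 70 for the primary comparison, 15% attrition, 86 recruited, 87.5% follow-up in earlier studies, two arms, product of coefficients.

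**Assumptions, because the plan is silent.** 1:1 allocation (37 per arm at 74); two-sided 0.05 and 80% power carried over from the primary calculation; residual SD of 1 for mediator and outcome; no direct effect of treatment; no covariates, no clustering by therapy group and no multiplicity adjustment across mediators.

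**Step 1: where 86 comes from.**
- 74 × 1.15 = 85.1, rounded up to 86. This reproduces the plan's number. Starting from 70 does not: 70 × 1.15 = 80.5, so 81.
- Dividing attrition out: 74/0.85 = 87.06, so 88 with equal arms.
- Expected remaining: 86 × 0.85 = 73.1, about 73.
- At 87.5% follow-up: 86 × 0.875 = 75.25, about 75.
- Primary requirement: 70/0.85 = 82.4, so 86 covers it.

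**Step 2: reproduce 74.** The model is M = aX + e and Y = bM + e, with both paths tested at two-sided 0.05 (joint significance). A medium regression effect is f² = 0.15, and √0.15 = 0.387, so a = b ≈ 0.39 per SD of X.
- Power at N = 74: 80.0% by joint significance, 81% by percentile bootstrap.
- Power at N = 73: 79.3%. The missing participant costs 0.7 points.

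So 74 is what this convention gives.

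**Step 3: put that on the treatment-group scale.** A 0/1 treatment with equal arms has SD 0.5, so moving from sham to active is 2 SD of X. Then d = 2 × 0.39 = 0.78 on the mediator. With d = 0.78 and b = 0.39, joint-significance power at 74 is 81%.

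**Step 4: first path alone, two-sample t-test, 37 per arm.**

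| d on mediator | Power |
|---|---|
| 0.50 | 56% |
| 0.66 | 80% |
| 0.78 | 91% |

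A joint test needs both paths to be significant, so these are ceilings whatever the second path is.

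**Step 5: mediated effect if medium means d = 0.5 between arms, N = 74.**

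| b | Test | Power |
|---|---|---|
| 0.30 | Joint significance | 39% |
| 0.39 | Joint significance | 50% |
| 0.59 | Joint significance | 56% |
| 0.39 | Percentile bootstrap | 52% |
| 0.39 | Bias-corrected bootstrap | 61% |
| 0.59 | Bias-corrected bootstrap | 63% |

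At N = 73 with b = 0.39, joint significance gives 49%. About 130 completers would be needed for 80% at d = 0.5 and b = 0.39.

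**The case against.** The strongest reply is that 74 is not an error. It gives 80% power under a recognised regression convention for medium, and the plan does not say that d = 0.5 was meant. This stands. A reader might infer that the mediation sample size has been shown to be wrong; the documents do not support that, because they define neither path.

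A reader might also infer that 80% power at 74 requires d of about 0.78 in every case. It does not: that value goes with b = 0.39. With d = 0.70 and b = 0.5, joint-significance power at 74 is 83%. The firm limit is the one from the first path alone, d of about 0.66.

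It is also tempting to call 0.78 implausible because it exceeds the pilot values of 0.64 and 0.43. Those are effects on drinking, not on any mediator, and they set no ceiling on the first path.

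On attrition, the plan only says that 86 allows for some loss. Earlier follow-up of at least 87.5% would leave about 75, and maximum likelihood would use partial records from people who miss the 2-month visit. These points make the slip harmless in practice, although the Participant Withdrawal section has the data of those who withdraw destroyed, so not every loss leaves a partial record. They do not make 86 consistent with 74 at the stated 15%.

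Finally, weekly mediator measurement, latent variables and covariate adjustment may raise power above these simulations. That is fair, but the plan does not say that any of them was used to reach 74.

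**Conclusion.** The point holds in two modest parts.

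The recruitment arithmetic is a small slip: 86 gives about 73 at 15% attrition, one below 74, where 88 would be needed. The power cost is under one point and the primary comparison is unaffected. That attrition was multiplied on is inferred from the match with 85.1; the plan does not show its formula.

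The mediation figure cannot be interpreted as written. The reading of medium that reproduces 74 implies about d = 0.78 between arms on the mediator when b is about 0.39. On a between-arm reading of d = 0.5, power is about 50% at b = 0.39, with a range of 39% to about 63% across the b values and tests tried. Under joint significance no second path brings it to 80%, because the first path alone has 56%. These figures rest on the assumptions listed with the calculation. They show how much turns on the missing definition; they do not show which definition was meant.

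**What to change.** Change the sample-size wording only:

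- State that 86 recruited leaves about 73 for analysis at 15% attrition, and that 88 would be needed for 74.
- State the two path values behind 74 on the treatment-group scale, for example d of about 0.78 on the mediator with a mediator-to-outcome path of about 0.39, if that is what was assumed. Add the test or bootstrap type used in the calculation.
- Report the power at d = 0.5 beside it, about 50% with a path of 0.39, so that a null mediation result is read as imprecise and not as evidence against the mechanism.

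The cost is a few sentences and a less favourable stated figure. Enrolment, design and analysis do not change.

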### I. *Target Population and Inclusion/Exclusion Criteria*

Participants for the proposed research include up to 350 individuals ages 18 and over who will be recruited from the Albuquerque Metropolitan Area using the following inclusion criteria:

- 1) interested in reducing alcohol drinking and consumed alcohol in past 30 days
- 2) right-handed
- 3) able to communicate in English

The inclusion criteria are based on our long-term goal of developing an intervention with broad appeal for most individuals who are interested in reducing drinking. The right-handed inclusion is based on the fact that the majority of people are right-handed and the effects of tDCS may be influenced by handedness (a proxy for hemispheric dominance; Schade et al., 2012). Ultimately we plan to develop separate tDCS montages that are specific to right and left hemisphere dominance, but for the purposes of this initial study we opted for increasing internal validity by excluding left-handed individuals.

The following exclusion criteria will be used for all participants

- (1) lifetime diagnosis of schizophrenia or bipolar disorder or current SUD other than nicotine or marijuana assessed via the phone screening questionnaire
- (2) cardiac pacemaker
- (3) implantable defibrillator
- (4) metal objects in upper body that might interfere with tDCS, or that tDCS may interfere with their function, including metal plates, screws and prosthetics in head, certain older tattoos and permanent makeup using metal containing inks, aneurysm clips, neural stimulators of any kind, ear implants or hearing aids, insulin pumps, drug infusion devices and dental appliances
- (5) for females, pregnant or attempting to get pregnant
- (6) history of seizures or seizure disorder
- (7) allergic to latex, rubber, conductive medium like saline or electrode gel
- (8) if assigned to active tDCS and unable to tolerate 1.5 mA of tDCS during a baseline stimulation session
- (9) history of severe alcohol withdrawal including tremors, seizures, or delirium tremens
- (10) currently or previously prescribed anti-seizure medications or medications for alcohol withdrawal
- (11) score of 8 or greater on the Clinical Institute Withdrawal of Alcohol Assessment Scale – Revised at any tDCS sessions
- (12) unable to attend treatment groups at scheduled time and unwilling to wait for group treatment at a time that works for the participant

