During each assessment period (i.e. baseline, end-of-treatment, and 2-month post-treatment follow-ups), self-report measures, and the EEG sessions will occur within one week of the self-report assessment on separate days or on a single day with a break between assessments. All assessments (behavioral, EEG) and treatment sessions will take place in the PCNC. The PCNC has three private assessment rooms to conduct behavioral assessments, as well as an EEG preparation room and shielded acquisition room.

Measure	Description/Purpose	Follow-up		
		Baseline	Post	2-Mo
Locator Form	Contact information for scheduling appointments	X	X	
Edinburgh Handedness scale	Right handedness (inclusion criteria)	X		
Electroencephalography (EEG)	Electrical activity of the brain	X	X	
Demographic form	Age, gender, education, ethnicity	X		
	Marital & employment status, income	X	X	X
Drinking History Questionnaire	Drinking history: onset, prior/current treatment	X	X	X
Form 90	Alcohol & illicit drug use, treatment seeking & AA	X	X	X
Structured Clinical Interview for DSM-IV modified for DSM-5 to include craving item	AUD diagnosis/comorbid SUD diagnoses	X	X	X
Short Inventory of Problems	Brief measure of alcohol-related problems	X	X	X
Penn Alcohol Craving Scale (PACS)	Self-reported craving for alcohol	X	X	X
Impaired Control Scale	Self-reported craving, difficulty controlling craving	X	X	X
International Affective Pictures Series (IAPS)	Behavioral measure cue/negative affect reactivity	X	X	X
UPPS Impulsive Behavior Scale	Urgency, lack of planning, perseveration	X	X	X
Stop Signal Task	Behavioral measure of cognitive control	X	X	X
Mindfulness daily practice tracking sheet	Current mindfulness practices	X	X	X
Breath Counting Tool	Behavioral measure of mindfulness	X	X	X
Toronto Mindfulness Scale	"State" mindfulness	X	X	X
NIH Emotions Toolbox	Social relationships, negative affect, and stress	X	X	X
NIH Cognition Toolbox	Executive function (shifting/attention), memory	X	X	X
Avoidance and Inflexibility Scale	Behavioral avoidance	X	X	X
Regulatory Flexibility Scale	Coping flexibility	X	X	X
Monetary Choice Questionnaire	Delay discounting	X	X	X
Treatment History Form	Assess ongoing treatment and prior/ongoing experience with meditation	X	X	X
Treatment Goals Form	Assess current treatment goal (e.g., controlled drinking, abstinence)	X	X	X
Applied Mindfulness Process Scale	Assess mindfulness skills learned during intervention		X	X

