Clinical Institute Withdrawal Assessment of Alcohol Scale, Revised	Measure of current alcohol withdrawal symptoms	X		
Blinding Questionnaire	One question assessing knowledge of condition		X	

**Primary Drinking Outcome.** The *Form 90* (Miller, 1996) is a semi-structured interview that gathers daily calendar-based alcohol and illicit drug use data. A 2-month assessment window will be used at each of the time-points. The *Form 90* will be used to derive estimates of the primary outcome: drinks per drinking day. The *Form 90* has demonstrated reliability in the collection of alcohol and drug use data (Maisto, Conigliaro, Gordon, McGinnis, & Justice, 2008; Sobell, Brown, Leo, & Sobell, 1996).

**Weekly During Treatment Measures.** An abbreviated assessment battery will be administered weekly during treatment to assess state mindfulness (Toronto Mindfulness Scale (Lau et al., 2006)), mindfulness practice in the prior week, craving (PACS; Flannery Volpicelli, & Pettinati, 1999), negative urgency and lack of planning items from the UPPS (Littlefield et al., 2015; Whiteside & Lynam, 2001), and negative affect (Short Forms of Anger, Sadness, Stress from NIH Emotions Toolbox; Salsman et al., 2013).

**Behavioral Tasks.** All behavioral tasks will be completed via computer during EEG to provide a measure of electrical brain activity during rest and completion of the tasks. To examine inhibitory control, we will use a *Stop Signal Task* (Logan, Van Zandt, Verbruggen, & Wagenmakers, 2014) in which participants make left-right judgments of the directionality of an arrow presented on the screen. For each trial, a circle will appear for 500 ms, followed by a left or right-pointing arrow for up to 1 second, and between 500 ms and 2500 ms jittered inter-trial interval to reduce anticipatory responses. Approximately 25% of trials will be "stop trials" with a tone played to signal participants to inhibit the

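### The primary model gives baseline drinks per drinking day no stated term, which risks losing precision that data already collected could supply

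*Combined protocol and SAP*

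**What the plan says.** The primary analysis is described only in the Data Analysis/Statistical Considerations section of the combined protocol and SAP. Under Aim #1 the efficacy model is "a generalized linear mixed model with drinks per drinking day at the end of treatment and follow-up as the primary outcomes". The covariates come from the paragraph on missing data: "Variables associated with missing data and those used in randomization (gender, age, treatment history) will be covaried in all analyses". Baseline drinking is not named there as a covariate, as a response or as part of a change score.

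Other places imply that baseline matters:

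- The power paragraph refers to "three time-points, we will need 70 participants to detect a medium effect".
- Aim #1 expects "significantly larger reductions in drinks per drinking day following treatment, as compared to sham tDCS".
- Hypothesis 1 in Objectives/Aims says that active tDCS "will be associated with significant reductions in drinks per drinking day after treatment and 2 months following treatment".
- Table 1 schedules Form 90 ("Alcohol & illicit drug use, treatment seeking & AA") at baseline, post-treatment and 2 months. The paragraph on the primary drinking outcome adds: "A 2-month assessment window will be used at each of the time-points".

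The baseline value of the primary outcome is therefore collected, and in the same form as the later values.

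**The concern.** In a small randomised trial, the baseline value of the outcome is usually the strongest available predictor of its later value. How it enters the model affects the standard error of the treatment comparison. The text allows at least three models: baseline left out, baseline as a repeated response with no constraint on its means, and baseline adjusted for or constrained equal across arms. The first two are valid under randomisation but less precise than the third. With 70 participants as the planning figure, precision should not be left to a choice made after the data are seen.

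A smaller matter sits in the same sentence. The rule on missingness covariates is mandatory, covers every analysis, and sets no limit on when the variable was measured. The trial records mindfulness, craving and negative affect weekly during treatment, and Hypothesis 2 names these as mediators of the tDCS effect. If one of them predicted missingness, the literal rule would put it in the primary model. The estimate would then no longer be the total effect of active versus sham tDCS.

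**Working it through.** **The plan's own figure.** The 70 cannot be reproduced from the stated inputs, because no correlation, no numeric value for the medium effect and no specific test are given. It can be matched only by supplying an unstated correlation. Taking f = 0.25, a between-arm repeated-measures test over three measures gives 70 at a correlation of 0.3 and 86 at 0.5. Taking d = 0.5, a baseline-adjusted comparison at one visit gives 70 at a correlation of about 0.667 (normal approximation). The 70 therefore does not show which model was intended, and nothing below depends on it.

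**Inputs for the precision check.** All are assumptions, since the documents give no variance or correlation: a linear model, 1:1 allocation, one post-baseline visit, equal variance at baseline and follow-up, and correlation rho between them of 0.3, 0.5 or 0.7.

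**Formulas.** The variance of the arm contrast, in units of its value when baseline is ignored, is:

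- baseline omitted: 1
- unconstrained change from baseline: 2(1 − rho)
- baseline as covariate, or as a repeated response with equal means: 1 − rho²

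A generalised least squares calculation for three visits under compound symmetry, with baseline means held equal, gives the same third row.

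| | rho = 0.3 | rho = 0.5 | rho = 0.7 |
|---|---|---|---|
| Omitted | 1 | 1 | 1 |
| Unconstrained change | 1.40 | 1.00 | 0.60 |
| Adjusted or constrained | 0.91 | 0.75 | 0.51 |
| Ratio, change to adjusted = 2/(1 + rho) | 1.54 | 1.33 | 1.18 |
| Ratio, omitted to adjusted = 1/(1 − rho²) | 1.10 | 1.33 | 1.96 |

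Taking square roots, confidence intervals would be wider than the adjusted ones by about 24%, 15% and 8% for unconstrained change, and by 5%, 15% and 40% for omission.

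**Does the second visit change this?** The plan models two post-baseline visits. If they are averaged under compound symmetry, the three variances become (1 + rho)/2, 1.5(1 − rho) and (1 + rho)/2 − rho². The ratio of change to adjusted is then 3/(1 + 2 rho) = 1.88, 1.50 and 1.25. The relative gain does not shrink.

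**Timing of the missingness covariates.** Exclusion (8) applies "if assigned to active tDCS and unable to tolerate 1.5 mA of tDCS during a baseline stimulation session", so assignment is already in force at that session. The recruitment section places the stimulation in the eligibility session. The data collection section allows EEG on a separate day within a week of the self-report measures, and the behavioural tasks are done during EEG. Some measures labelled baseline could therefore follow active stimulation. A cut-off at the baseline visit would not exclude them, but a cut-off before the stimulation session would.

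**The case against.** The best reply is that baseline does have a role. Form 90 supplies the primary outcome at every time-point, the power paragraph counts three of them, and the hypotheses speak of reductions. Read together, these make baseline an occasion of the outcome. That is a fair reading, and it is why the point is about a missing model term and constraint rather than neglect of baseline. It does not settle the matter, because the model sentence names only the two later visits and no text says that baseline means are held equal. That the model would be unconstrained is also an inference. If the team intends adjustment or equal means, the loss is zero.

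A reader might infer more than the documents support, in three ways:

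- **That the trial is underpowered, or reaches 80% power only at a high correlation.** Single-visit power at d = 0.5 and 70 participants is 0.58, 0.66 and 0.82 with adjustment at the three correlations. Averaging both visits under compound symmetry gives 0.79, 0.83 and 0.93. The effect size and correlation are assumed, and the generalized linear mixed model has no stated link. These are not the trial's power.
- **That the treatment comparison is biased by the handling of baseline.** It is not. Randomisation protects all three models, and only precision differs.
- **That treatment-affected variables will be covaried.** No text says so. Baseline correlates of attrition are the natural reading. The rule also covers the mediation analyses, where covarying the mediators under it would make little sense. What remains is an ambiguity to close.

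**Conclusion.** The point stands as an avoidable risk to precision. As written, the primary model neither adjusts for baseline drinks per drinking day nor constrains its means, although the value is collected at no extra cost. Relative to adjustment, the single-visit variance would be 1.18 to 1.54 times as large under unconstrained change, and 1.10 to 1.96 times as large if baseline is omitted, for correlations of 0.3 to 0.7. These ratios rest on a linear model and an assumed correlation, and may not carry over exactly to the planned model. The loss is nil if the intended analysis already uses one of the two efficient forms. The open wording on missingness covariates is a minor clarification; the size and sign of any shift from it are unknown.

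**What to change.** Add to the Aim #1 analysis:

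> The primary generalized linear mixed model of drinks per drinking day at end of treatment and 2 months adjusts for baseline drinks per drinking day, gender, age and treatment history (or includes baseline as a repeated response with means constrained equal across arms).

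One of the two forms should be chosen in advance. This needs only SAP wording and no new data. Baseline Form 90 looks back 2 months, so even if the interview came after the brief stimulation session, any effect on the recorded value would be small.

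As a minor clarification, limit missingness-related covariates in the treatment-effect model to measures taken before the baseline stimulation session. Later predictors of missingness should be used, if at all, only in a sensitivity analysis such as multiple imputation. That adds a small amount of analysis work.
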